Appendix 5 Toxicity Criteria for Laboratory Biochemistry Parameters based on CTCAE version 5.0

Laboratory Toxicity	Grade 1	Grade 2	Grade 3	Grade 4
Chemistry				
Sodium Increased (Hypernatremia)	>ULN - 150 mmol/L	>150 - 155 mmol/L	>155 - 160 mmol/L	>160 mmol/L
Sodium Decreased (Hyponatremia)	<LLN - 130 mmol/L		<130 - 120 mmol/L	<120 mmol/L
Potassium Increased (Hyperkaliemia)	>ULN - 5.5 mmol/L	>5.5 - 6.0 mmol/L	>6.0 - 7.0 mmol/L	>7.0 mmol/L;
Potassium Decreased (Hypokaliemia)	<LLN - 3.0 mmol/L	<LLN - 3.0 mmol/L	<3.0 - 2.5 mmol/L	<2.5 mmol/L
Calcium Increased (Hypercalcemia)	>ULN - 11.5 mg/dL; >ULN - 2.9 mmol/L Ionized calcium >ULN - 1.5 mmol/L	>11.5 - 12.5 mg/dL; >2.9 - 3.1 mmol/L Ionized calcium >1.5 - 1.6 mmol/L	>12.5 - 13.5 mg/dL; >3.1 - 3.4 mmol/L; Ionized calcium >1.6 - 1.8 mmol/L	>13.5 mg/dL; >3.4 mmol/L; Ionized calcium >1.8 mmol/L
Calcium Decreased (Hypocalcemia)	<LLN - 8.0 mg/dL; <LLN - 2.0 mmol/L; Ionized calcium <ULN - 1.0 mmol/L	<8.0 - 7.0 mg/dL; <2.0 - 1.75 mmol/L Ionized calcium <1.0 - 0.9 mmol/L	<7.0 - 6.0 mg/dL; <1.75 - 1.5 mmol/L; Ionized calcium <0.9-0.8 mmol/L	<6.0 mg/dL; <1.5 mmol/L; Ionized calcium <0.8 mmol/L
Albumin Decreased (hypoalbuminemia)	<LLN - 3 g/dL; <LLN - 30 g/L	<3 - 2 g/dL; <30 - 20 g/L	<2 g/dL; <20 g/L	
Alkaline Phosphatase increased	>ULN - 2.5 x ULN if baseline normal 2.0 - 2.50 x baseline if baseline abnormal	>2.5 - 5.0 x ULN if baseline normal >2.5 - 5.0 x baseline if baseline abnormal	>5.0 - 20.0 x ULN if baseline normal >5.0 - 20.0 x baseline if baseline abnormal	>20.0 x ULN if baseline normal 20.0 x baseline if baseline abnormal
Alanine amino transferase increased	>ULN - 3.0 x ULN if baseline normal 1.5 - 3.0 x baseline if baseline abnormal	> 3.0 - 5.0 ULN if baseline normal >3.0 - 5.0 x baseline if baseline abnormal	>5.0 - 20.0 x ULN if baseline normal >5.0 - 20.0 x baseline if baseline abnormal	>20.0 x ULN if baseline normal > 20.0 x baseline if baseline abnormal
Aspartate amino transferase increased	>ULN - 3.0 x ULN if baseline normal 1.5 - 3.0 x baseline if baseline abnormal	> 3.0 - 5.0 ULN if baseline normal >3.0 - 5.0 x baseline if baseline abnormal	>5.0 - 20.0 x ULN if baseline normal >5.0 - 20.0 x baseline if baseline abnormal	>20.0 x ULN if baseline normal > 20.0 x baseline if baseline abnormal
Blood Bilirubin Increased	>ULN - 1.5 x ULN if baseline normal >1.0-1.50 x baseline if baseline abnormal	>1.5 - 3.0 x ULN if baseline normal >1.5-3.0 x baseline if baseline abnormal	>3.0 - 10.0 x ULN if baseline normal >3.0- 10.0 x baseline if baseline abnormal	>10.0 x ULN if baseline normal > 10.0 x baseline if baseline abnormal

Gamma Glutamyl Transferase Increased	>ULN - 2.5 x ULN if baseline normal 2.0 - 2.5 x baseline if baseline abnormal	>2.5 - 5.0 x ULN if baseline normal >2.5 - 5.0 x baseline if baseline abnormal	>5.0 - 20.0 x ULN if baseline normal >5.0 - 20.0 x baseline if baseline abnormal	>20.0 x ULN if baseline normal >20.0 x ULN if baseline abnormal
Creatinine Increased	>ULN – 1.5 x ULN	>1.5 - 3.0 x baseline; >1.5 – 3.0 x ULN	>3.0 baseline; >3.0 – 6.0 x ULN	>6.0 x ULN
Chronic Kidney Disease	eGFR (estimated Glomerular Filtration Rate) or CrCl (creatinine clearance) <LLN - 60 ml/min/1.73 m ² or proteinuria 2+ present; urine protein/creatinine >0.5	eGFR or CrCl 59 - 30 ml/min/1.73 m ²	eGFR or CrCl 29 - 15 ml/min/1.73 m ²	eGFR or CrCl <15 ml/min/1.73 m ²
Hypoalbuminemia	<LLN - 3 g/dL; <LLN - 30 g/L	<3 - 2 g/dL; <30 - 20 g/L	<2 g/dL; <20 g/L	
Proteinuria	1+ proteinuria	2+ and 3+ proteinuria	4+ proteinuria	

Appendix 6 Abnormality Criteria

Hepatic abnormality criteria		
Hepatic laboratory Parameters	Abnormality criteria	
ALT	> 3 x ULN	
	> 5 x ULN	
	> 8 x ULN	
	> 10 x ULN	
	> 20 x ULN	
AST	> 3 x ULN	
	> 5 x ULN	
	> 8 x ULN	
	> 10 x ULN	
	> 20 x ULN	
ALP	> 1.5 x ULN	
	> 2 x ULN	
	> 3 x ULN	
Total bilirubin	> 1.5 x ULN	
	> 2 x ULN	
	> 3 x ULN	
	> 5 x ULN	
GGT	> 1 x ULN	
Blood pressures and pulse rate abnormality criteria		
Blood pressures and pulse rate criteria	Abnormality criterion value	Abnormality criterion on change from baseline
SBP	> 180 mmHg	≥ 20 mmHg increase from baseline
	< 90 mmHg	≥ 20 mmHg decrease from baseline
DBP	> 105 mmHg	≥ 15 mmHg increase from baseline
	< 50 mmHg	≥ 15 mmHg decrease from baseline
Pulse rate	> 120 bpm	≥ 10 bpm increase from baseline
	< 50 bpm	≥ 10 bpm decrease from baseline
Weight Abnormality Criteria		
Weight criteria	Abnormality criteria	
Weight (kg)	≥ 7% increase from baseline	
	≥ 7% decrease from baseline	
ECG abnormality criteria		
ECG criteria	Abnormality criteria	

QTcF interval prolongation*	> 450 msec
	> 480 msec
	> 500 msec
Change from baseline in QTcF interval*	> 30 msec increase from baseline
	> 60 msec increase from baseline
PR interval	< 120 msec
	> 200 msec
QRS complex	< 80 msec
	> 120 msec
HR	< 60 bpm
	> 100 bpm

ALT = alanine aminotransferase; AST = aspartate aminotransferase; ALP = alkaline phosphatase; GGT= gamma-glutamyl transferase; SBP = Systolic blood pressure; DBP = diastolic blood pressure; bpm=beats per minutes to be classified as potentially clinically significant, the measurement must satisfy both criteria: the criterion for the value and the criterion for the change relative to baseline.

**Abnormal QTcF interval categories as defined in ICH Guidelines E14*

Any patients fulfilling at least one ECG abnormality criteria (as described in [Appendix 6](#) Abnormality Criteria or having at least one abnormal ECG assessed as significant by the investigator will be listed presenting all his/her ECG information.

Appendix 7 Prohibited medication solely metabolized by UGT1A9 and UGT2B7 and determination criteria

Examples of medications that are solely metabolized by UGT1A9 and UGT2B7 and prohibited for the duration of the trial are provided below.

Medications solely metabolized by UGT1A9		Medications solely metabolized by UGT2B7		
Medication name	ATC code	Medication name	ATC code	Comments
Flavopiridol		Benoxyprofen	M01AE06	
Propofol	N01AX10	Carbamazepine	N03AF01	
		Codeine	R05DA12 R05DA04 N02AJ01 N02AJ02 N02AJ03 N02AJ07 N02AJ08 N02AJ09 N02AA08 N02AA58 N02AA59 N02AA79	
		Cyclosporin A	L04AD01, S01XA18	
		Epirubicin	L01DB03	
		Indomethacin	C01EB03 M01AB01 M01AB51 M02AA23 S01BC01 S01CC02	S01CC02 also contains anti-infective medications
		Tacrolimus	D11AH01 L04AD02	
		Tiaprofenic acid	M01AE11	
		Zaltoprofen		Not popped up in ATC code list.
		Zomepirac	M01AB04	
		Zidovudine	J05AF01 J05AR01 J05AR04 J05AR05	Combination product Combination product Combination product

ATC = Anatomic Therapeutic Class

Appendix 8 Prohibited medications strong CYP3A4 inducers and determination criteria

Strong CYP3A4 inducers		
Medication name	ATC code	Comments
Rifampicin	J04AB02 J04AB03 J04AM02 J04AM05 J04AM06 J04AM07 A07AA13* D06AX15* S01AA16* S02AA12*	This is a list on rifampicin only but also on products which contain rifampicin * refers to rifamycin
carbamazepine	N03AF01	
phenytoin	N03AB02 N03AB04 N03AB05 N03AB52	
phenobarbital,	N03AA01 N03AA02	
Primidone	N03AA03	
St John's Wort (hypericum perforatum)		Not popped up in ATC code list.

ATC = Anatomic Therapeutic Class

Appendix 9 Other Prohibited medications and determination criteria

Other prohibited medication			
Medication name	ATC code	Verbatim code	Comments
Nabiximols, cannabis or cannabinoid-based derived product	N03AX24		N03AX24: group of other anti-epileptics and cannabidiol is one of them
	N02BG10		This is the greater group of analgesics, and N02BG10 is a cannabinoid
Botulinum toxin injections,	M03AX01	Contains: ‘BO’ and ‘Tox’ “Dysport ‘Xeomin	Muscle relaxant products
Antipsychotic medications,	N05A apart from N05AN (Lithium) Including N05AH02 (BDZ)		
Benzodiazepines (if not following protocol requirements)	N03AE N05BA N05CD M03BX07		N03AE: clonazepam N05BA: broader group of anxiolytics contain the main used BDZ N05CD broader group of hypnotics but also contains melatonin for instance. M03BX07: tetrazepam

BDZ=Benzodiazepines

Appendix 10 Medications used in MS and determination criteria

Any medication used for MS along with its category will be retrieved from the eCRF Concomitant medication form. However, the information in the table below will be used to define subcategory of interest.

MS medications type	WHO-DD Therapeutic class	Standardized Medication name	ATC code	Verbatim term	Comments
Antispasticity medication	Muscle relaxant (M03)	Baclofen	M03BX01	Contains: 
“BACLOFEN”	
		Tizanidine	M03BX02	Contains: 
“TIZANIDINE”	
		Dantrolene	M03CA	Contains: 
‘DANTROLENE’	
		Tetrazepam (BDZ)	M03BX07		Not considered as a BDZ in the coding of ATC, but as a centrally acting muscle relaxant.
		Botulinum toxin	M03AX01	Contains: 
‘BO’ and ‘Tox’Dysport‘Xeomin’	
	Antiepileptic (N03)	Others	M03B and M03C apart those mentioned above		Refers to the broader group of muscle relaxants
		Clonazepam	N03AE		N03AE is a BDZ
		Gabapentin	N03AX12		
		Pregabalin	N03AX16		
	Psychoanaleptic (N05)	Cannabinidiol	N03AX24		Not allowed per protocol
		Clozapine (BDZ)	N05AH02		
		Benzodiazepines	N05BA N05CD		N05BA and N05CD refers to a list of BDZ
Medication to treat other MS symptoms	Other system nervous system drug (N07)	Dalfampridine	N07XX007		
		Fampridine	N07XX007		

MS=Multiple sclerosis; ATC= Anatomic Therapeutic Class; BDZ=Benzodiazepines

Appendix 11 Adverse Drug Reaction of Special Interest – AE selections

Adverse drug of special interest type	AESI search
Falls and injuries	PT from either: SOC "Injury, Poisoning, and procedural complications" Accidents and injuries (SMQ) [20000135]
Drug reaction with eosinophilia and systemic systems (DRESS)	See Appendix 13 Modify registry of severe cutaneous adverse reaction criteria for Drug reaction with eosinophilia and systemic systems (DRESS)
Disorientation and confusion	Confusion and disorientation High Level Term (HLT) [10010301]
Driving and road traffic accident	Impaired driving ability (PT) [10049564] Road traffic accident (PT) [10039203] Impaired ability to use machinery (PT) (10077474) Accident – for machinery (PT) (10000369)
Abuse liability	Drug abuse, dependence and withdrawal (SMQ) [20000100] Euphoric mood (PT) [10015535]
Abnormal liver adverse events	Drug related hepatic disorders – comprehensive search (SMQ) [20000006] Drug related hepatic disorders – severe events only (SMQ) [20000007]
Somnolence and sedation	Somnolence (PT) [10041349] Hypersomnia (PT) [10020765] Sedation (PT) [10039897]
Fatigue and lethargy	Fatigue (PT) [10016256] Lethargy (PT) [10024264]
Suicidal ideation and behavior	Suicide/self-injury (SMQ) [20000037] AEs will also be searched using the following search term string of suicidality-related terms (Bangs, 2008): accident, asphyxiation, burn, cut, drown, firearm, die, dying, gas, gun, hang, hung, immolat, injur, jump, attempt, kill, monoxide, mutilate, overdos, poison, self-damag, self-harm, self injur, shoot, slash, suffocation, and suic.
Significant cardiovascular (CVD) disease	Cardiac arrhythmias (SMQ) [20000049] Cardiac failure (SMQ) [20000004] Cardiomyopathy (SMQ) [20000150] Hypertension (SMQ) [20000147] Ischaemic heart disease (SMQ) [20000043] Pulmonary hypertension (SMQ) [20000130]
Cognitive function	Cognitive and attention disorders and disturbances High Level Group Term (HGLT) [10009841]
Depression and depressed mood	Depression (excl. suicide and self-injury) (SMQ) [20000167]
Psychosis and psychotic disorders	Psychosis and psychotic disorders (SMQ) [20000117] Disturbances in thinking and perception (HGLT) [1001351]
Seizures	Convulsions (SMQ) [20000079] (includes Seizure [PT]) [10039906]

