12.7.2.3 Adverse Events of Special Interest

An adverse events of special interest (AESI) is any adverse event of scientific or medical interest to the study medication. The types of AESIs which will be analyzed are presented in **Descriptive presentations of AESIs** will be given for each AESI category on the safety analysis set presenting:

- The number and percentage of patients with at least one treatment-emergent AESI,
- The number and percentage of patients with at least one treatment-emergent AESI by SOC and PT,
- The number and percentage of patients with at least one severe treatment-emergent AESI,

- The number and percentage of patient with at least one serious treatment-emergent AESI,
- The number of and percentage of patients with at least one treatment-emergent AESI leading to permanent IMP discontinuation,
- The number of treatment-emergent AESI,
- The number of severe treatment-emergent AESI,
- The number of serious treatment-emergent AESI,
- The number of treatment-emergent AESI leading to permanent IMP discontinuation,
- The number of unique* treatment-emergent AESI,
- The number of unique* severe treatment-emergent AESI,
- The number of unique* serious treatment-emergent AESI,
- The number of unique* treatment-emergent AESI leading to permanent IMP discontinuation,
- The time to first onset of treatment-emergent AESI categorized as :1-7 day, 8 to 14 days, 15 to 21 days, 21 to 28 days and > 28 days (as described in [Section 10.21.3](#)),

**Unique AESI is defined as any AESI coded with the same PT and having the same date of onset.*

Analysis of time to first onset of AESIs will be conducted by actual treatment arm on the Safety Analysis SAS using the SAS® LIFEEST procedure.

Assuming no carry over effect, Kaplan-Meier plots (estimates) of cumulative incidence of first onset of AESI will be provided by actual treatment arm on the Safety analysis set. The time to AESI onset (in days) is defined as the number of days from 1st IMP intake of the treatment arm (e.g., nabiximols, placebo) the AESI is emergent to (as defined in [Section 12.7.1](#)) until the onset of the AESI (see detailed in [Section 10.21.4](#)).

For patients not known to have experienced an AESI during respectively Period 1 and Period 2:

- Period 1 censoring day is the date of 1st IMP intake during Period 2 minus 1 day for those patients continuing in Period 2 and, the end of study date for those patients who discontinued before Period 2,

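### The text-string search for the suicidality AESI brings non-suicidal events, such as road traffic accidents, into the counts, and the SAP has no step to review or remove them

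*SAP*

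**What the plan says.** SAP Appendix 11 is titled "Adverse Drug Reaction of Special Interest – AE selections" and gives one selection rule per AESI category. For suicidal ideation and behavior the rule has two parts. The first is the Suicide/self-injury SMQ. The second reads "AEs will also be searched using the following search term string of suicidality-related terms". The string starts "accident, asphyxiation, burn, cut, drown, firearm, die, dying, gas, gun, hang, hung, immolat, injur" and ends "overdos, poison, self-damag, self-harm, self injur, shoot, slash, suffocation, and suic". A 2008 publication is cited for it.

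The same appendix has a driving category, which lists 'Road traffic accident' and 'Accident' as preferred terms, and a falls-and-injuries category, which takes the whole injury SOC plus an accidents-and-injuries SMQ.

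SAP 12.7.2.3 uses the selected events directly. For each category it plans "The number and percentage of patients with at least one treatment-emergent AESI", then severe events, serious events, events leading to permanent discontinuation of IMP, time to first onset, and Kaplan-Meier plots by actual treatment arm. A plot is made only if more than 5 patients in each arm have an event. SAP 12.7.1.1 adds a row for any TEAE of special interest and a count of such TEAEs.

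The SAP addendum (section 7.0) appears to keep TEAE and C-SSRS reporting as the SAP set it out; the table layout is broken in the text available.

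**The concern.** A string list of this kind is built for sensitivity. It finds candidates that someone then reads. Appendix 11 places it in a selection table, and nothing between that table and the counts removes a hit with no suicidal content. A reader of the safety tables would take the suicidality row to mean suicidality, while some of its entries could be traffic accidents or gastrointestinal events.

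The SAP treats driving accidents and injuries as separate AESIs for this drug. If the arms differed in accidents, the same difference would reappear under suicidality. False hits also count toward the threshold that triggers the Kaplan-Meier plot.

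**Working it through.** The plan states no figure here to reproduce. The check is to match the 28 strings against event terms under each rule the SAP could mean.

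**Inputs.** The strings come from Appendix 11. Event terms come from Appendix 11 (driving category) and Appendix 13.2 (the DRESS organ list). A few ordinary terms are my own assumptions and are marked so.

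**Rules.** The SAP names none, so three were tried: whole word, start of word (stem), and anywhere inside a word. Several strings are truncated (*injur*, *immolat*, *overdos*, *self-damag*, *suic*). They cannot work as whole words, so at least stem matching must be intended. They do not show that matching inside a word is intended.

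| Term | Source | Whole word | Stem | Inside word |
|---|---|---|---|---|
| Road traffic accident | Appendix 11 | accident | accident | accident |
| Accident | Appendix 11 | accident | accident | accident |
| Hepatocellular injury | Appendix 13.2 | none | injur | injur |
| Gastritis | Appendix 13.2 | none | gas | gas |
| Vasculitis gastrointestinal | Appendix 13.2 | none | gas | gas |
| Hepatitis acute | Appendix 13.2 | none | none | cut |
| Limb injury, Head injury | assumed | none | injur | injur |
| Gastroenteritis | assumed | none | gas | gas |
| Burning sensation | assumed | none | burn | burn |
| Acute sinusitis | assumed | none | none | cut |
| Fall, Contusion, Laceration, Ankle fracture, Ligament sprain, Skin abrasion | assumed | none | none | none |

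Two of the four terms in the SAP's own driving category therefore enter the suicidality category whichever rule is used.

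**From hit to count.** Appendix 11 does not say whether the preferred term or the investigator's term is searched, and gives no exclusion. Section 12.7.2.3 goes straight to counting. The C-SSRS is analyzed separately in 12.7.5.3 and is not used to confirm AE hits.

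**Comparison within the SAP.** Other searches are better specified. The COVID-19 rule (10.21.2) names the fields and excludes a negative test. The DRESS skin search (Appendix 13.1) names the SOC and preferred terms, and DRESS requires at least 3 criteria (Appendix 13).

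**Effect on the overall AESI row.** A road traffic accident is already an AESI through the driving category, so it adds no patient to the any-AESI row. A hit that belongs to no other category does. 'Gastritis' is an example, since alone it cannot meet the DRESS rule.

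**The case against.** The other side has several good points.

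- Appendix 11 says that events will be searched, not that every hit is a case. Counting every hit follows from the absence of a review step. The cited 2008 source may describe case review; that cannot be checked here.
- Each category is also tabulated by SOC and PT, and AESIs are listed with the investigator's term (12.7.1), so 'Gastritis' or 'Road traffic accident' would be visible as such. The C-SSRS gives prospective suicidality endpoints that do not depend on the string.
- AESI categories need not be mutually exclusive, and a deliberately sensitive safety search is legitimate.

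All of this stands, and it limits the harm. It does not put a review step into the SAP: a programmer following the appendix would still count these hits as suicidality.

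A reader might infer more than the documents support:

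- *Every injury and every acute event is counted.* Fall, contusion, laceration and fracture match no string. 'Acute' terms match only under an inside-word rule that the SAP does not state for this search, although its medication searches in Appendices 9 and 10 do use a contains rule.
- *The category would consist mostly of falls.* 'Fall' does not match.
- *Time to onset is tested between arms.* Section 12.7.2.3 plans Kaplan-Meier estimates with Greenwood intervals and names no test.
- *A numerical inflation factor.* Any such multiple is the ratio of two assumed event rates, because the documents give neither.
- *A real signal would be lost.* The PT tables, listings and C-SSRS make that unlikely.

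**Conclusion.** The point holds. Following the selection rule as written puts non-suicidal events into the suicidality AESI counts and plot and can raise the overall count of TEAEs of special interest. For 'Road traffic accident' and 'Accident' this needs no assumption about matching. For terms containing 'injury' or starting with *gas* it needs only the stem matching that the truncated strings require. It also rests on reading the absence of a review step in the SAP as the absence of one in practice.

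The size is unknown: it depends on how many such events occur, and the trial stopped before full recruitment. The effect is confined to AESI safety outputs; the primary and secondary efficacy analyses are untouched. This should be fixed, because suicidality is a sensitive label and the correction is small.

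**What to change.** Amend Appendix 11 in three ways before unblinding:

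1. State which field is searched (preferred term, investigator's term or both) and the matching rule.
2. Use the string search only to produce a listing, reviewed by the medical monitor blinded to treatment sequence.
3. In the 12.7.2.3 tables and plot, and in the 12.7.1.1 AESI rows, count under this category only Suicide/self-injury SMQ events plus string hits that the review confirms. Keep unconfirmed hits in the listing.

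This keeps the search's sensitivity, which restricting the category to the SMQ alone would give up. The cost is a short SAP edit and a review of one listing by the existing medical monitor. No new data are needed.

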Appendix 12 Category of Adverse Events of Special Interest

List number	Category of adverse events of special interest
01	Falls and injuries
02	Drug reaction with eosinophilia and systemic systems
03	Disorientation and confusion
04	Driving and road traffic accident
05	Abuse liability
06	Abnormal liver adverse events
07	Somnolence and sedation
08	Fatigue and lethargy
09	Suicidal ideation and behavior
10	Significant cardiovascular disease
11	Cognitive function
12	Depression and depressed mood
13	Psychiatric disorders
14	Seizures

Appendix 13 Modify registry of severe cutaneous adverse reaction criteria for Drug reaction with eosinophilia and systemic systems (DRESS)

Only patients meeting the criteria will be presented.

At least 3 of the following criteria should be present for hypersensitivity syndrome or DRESS:

- 1. Acute skin rash
- 2. Involvement of at least 1 internal organ
- 3. Enlarged lymph nodes of at least 2 sites
- 4. One of the following blood count abnormalities (limits provided by laboratory):
 - lymphocytes above or below the laboratory limits
 - eosinophils above the laboratory limits (in % or absolute count)
 - platelets below the laboratory limits
- 5. Fever above 38 degrees Celsius

The adverse events should occur within 30 days of each other (There should be temporal proximity for the onset of these AEs.). Some PTs may be mentioned in more than one SOC. (within 1 month of each other).

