Appendix 13.2 Involvement of at least 1 internal organ

Blood and lymphatic system disorders SOC	Cardiac disorders SOC:	Endocrine disorders SOC:
Agranulocytosis Aplastic anemia Aplasia pure red cell Autoimmune lymphoproliferative syndrome Autoimmune neutropenia Autoimmune pancytopenia Blood disorder Bone marrow disorder Bone marrow failure Bone marrow toxicity Coagulopathy Disseminated intravascular coagulation Disseminated intravascular coagulation in newborn Drug reaction with eosinophilia and systemic symptoms Eosinophilia Febrile neutropenia Granulocytopenia Haemolytic anemia Hemolysis Hypereosinophilic syndrome Leukemoid reaction Leukopenia Lymphocytosis Lymphopenia Hypersensitivity vasculitis Lymphadenitis Lymphadenopathy Lymphoma Monocytosis Mononucleosis Neutropenia Pancytopenia Platelet disorder Platelet toxicity Splenitis Splenomegaly Splenosis Thrombocytopenia	Autoimmune myocarditis Cardiomyopathy Endocarditis Eosinophilic myocarditis Myocarditis Pericarditis Pericardial effusion Pericardial disease Pleuropericarditis	Adrenalitis Autoimmune thyroiditis Thyroiditis

Eye disorders SOC	Gastrointestinal disorders SOC	Hepatobiliary disorders SOC
Eye allergy	Allergic colitis	Autoimmune hepatitis
Eye swelling	Colitis	Amylase increased
Iritis	Eosinophilic colitis	Blood trypsin increased
Iridocyclitis	Eosinophilic oesophagitis	Cholangitis
Optic neuritis	Gastritis	Cholecystitis
Retinitis	Gingival edema	Hepatic failure
Uveitis	Gingival swelling	Hepatic functional abnormal
Vitritis	Gingivitis	Hepatic encephalopathy
Scleritis	Glossitis	Hepatic infiltration eosinophilic
	Enteritis	Hepatitis
	Mouth ulceration	Hepatitis acute
	Mesenteritis	Hepatitis toxic
	Edema mouth	Hepatocellular injury
	Oropharyngeal swelling	Hepatomegaly
	Parotitis	Hepatosplenomegaly
	Pancreatitis	Hepatorenal failure
	Periodontitis	Hepatorenal syndrome
	Sialadenitis	Hepatotoxicity
	Stomatitis	Hyperbilirubinemia
	Swollen tongue	Hyperbilirubinemia neonatal
	Tongue oedema	Hyperlipidemia
	Vasculitis gastrointestinal	Jaundice
		Jaundice neonatal
		Liver disorder
		Lipase abnormal
		Lipase increased
		Edema due to hepatic disease
		Edematous pancreatitis
		Pancreatic enzymes increased
		Pancreatic hemorrhage
		Pancreatic necrosis
		Pancreatitis (any PT that includes the word "pancreatitis")
		Pancreatorenal syndrome
		Peripancreatic fluid collection
		Swollen tongue

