Appendix 13.3 Enlarged lymph nodes of at least 2 sites

Search for PT including the word “Lymphadenopathy” alone or as part of another PT

Such as some examples are given below:

- Lymphadenopathy Mediastinal
- Paratracheal Generalized
- Retroperitoneal
- Vaccination site

Search for other PT that could reflect lymphadenopathy

- Benign lymph node neoplasm
- Lymph node palpable
- Lymph node scan abnormal

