Appendix 13.4 One of the following blood count abnormalities

The search will use laboratory blood sample values along with their corresponding reference ranges

- Lymphocytes above or below lab limits
- Eosinophils above the lab limits
- Platelets below lab limits

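### SAP Appendix 13 lets one finding score two of the five DRESS criteria, while an adverse event coded as DRESS scores only one

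*SAP*

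**What the plan says.** SAP Appendix 11 gives a search for each adverse event category of special interest. For DRESS it names no preferred term and only refers onward: "See Appendix 13 Modify registry of severe cutaneous adverse reaction criteria".

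Appendix 13 sets five criteria: (1) acute skin rash, (2) involvement of an internal organ, (3) enlarged lymph nodes, (4) a blood-count abnormality, (5) fever. The threshold is "At least 3 of the following criteria should be present for hypersensitivity syndrome or DRESS", rash is not mandatory, and the events should fall within 30 days of each other. The output is filtered: "Only patients meeting the criteria will be presented".

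The criteria are then turned into searches:

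- 13.1 (skin) is a list of skin terms plus any term containing rash or dermatitis.
- 13.2 (organ) is a long list by system organ class. Its blood and lymphatic column includes "Lymphocytosis Lymphopenia Hypersensitivity vasculitis Lymphadenitis Lymphadenopathy", as well as Eosinophilia, Thrombocytopenia, Febrile neutropenia and "Drug reaction with eosinophilia and systemic symptoms". The DRESS term is listed again under immune system disorders. Abnormal haematology investigation terms are also accepted.
- 13.3 is headed "Enlarged lymph nodes of at least 2 sites", but the search beneath it accepts any term containing the word lymphadenopathy, plus three other node terms.
- 13.4 uses laboratory values only, for example "Lymphocytes above or below lab limits", high eosinophils or low platelets.
- 13.5 uses adverse event terms, including any that contain the word febrile.

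The only remark on overlap is that a term may occur in more than one system organ class. Nothing is said about a term that occurs under more than one criterion.

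**The concern.** A rule of three out of five is meant to require three separate signs. If one sign can fill two places, the rule becomes two signs for that patient. If the diagnosis itself fills only one place, a patient whom the investigator has already diagnosed can fall below the threshold.

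SAP Section 12.7.2.3 reports patient counts and percentages for each special-interest category, with time to onset by actual treatment arm, and describes no medical review of the selected cases. The DRESS count could therefore include patients with a febrile illness and a changed blood count, and leave out a reported DRESS. If the category holds only a few patients, one such error changes the comparison between arms.

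**Working it through.** There is no stated figure to reproduce. The check is to score sets of findings against the lists in 13.1 to 13.5, all within the 30-day window, and to call a case at 3 or more. The last column applies the proposed fix: one event with its own laboratory value counts once, the two-site rule is applied, and the DRESS term is selected directly.

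| Findings on record | Criteria met as written | As written | After the fix |
|---|---|---|---|
| Lymphadenopathy | 2, 3 | 2 of 5, no | no |
| Lymphadenopathy + Pyrexia | 2, 3, 5 | 3 of 5, case | at most 2, no |
| Lymphopenia + its own low value + Pyrexia | 2, 4, 5 | 3 of 5, case | 2, no |
| Thrombocytopenia + its own low value + Pyrexia | 2, 4, 5 | 3 of 5, case | 2, no |
| Febrile neutropenia | 2, 5 | 2 of 5, no | 1, no |
| Febrile neutropenia + one out-of-range lymphocyte, eosinophil or platelet value | 2, 4, 5 | 3 of 5, case | 2, no |
| DRESS term alone | 2 | 1 of 5, not presented | selected |
| DRESS term + Rash | 1, 2 | 2 of 5, not presented | selected |
| DRESS term + abnormal blood count | 2, 4 | 2 of 5, not presented | selected |
| DRESS term + Rash + Pyrexia | 1, 2, 5 | 3 of 5, case | selected |
| Rash + Hepatitis + Pyrexia | 1, 2, 5 | 3 of 5, case | 3, case |

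The last row is a control: three separate findings remain a case.

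The lymphadenopathy row depends on how 13.3 is programmed. As written, the search counts no sites, so a single term scores criterion 3. If the heading is enforced, single-site nodes plus fever meet criteria 2 and 5 only (2 of 5). Nodes at two sites, or generalized nodes, coded to the listed term plus fever still meet 2, 3 and 5 (3 of 5). Enforcing the heading alone therefore does not remove the double scoring. Note also that 13.2 lists the bare term ("Lymphadenitis Lymphadenopathy Lymphoma Monocytosis"), so a site-qualified term scores criterion 2 only if that entry is read as a word search.

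The DRESS rows follow by elimination. The term is in 13.2 and in no other list. It contains neither rash nor dermatitis (13.1), nor lymphadenopathy (13.3), nor febrile (13.5), and 13.4 does not read event terms. Listing it under two system organ classes within 13.2 still gives one criterion.

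Protocol Section 12.6 A makes the missing components more likely. Once a diagnosis is made, the eCRF entry is changed from the symptoms to the diagnosis. Symptoms may sometimes be kept in the verbatim description, but the plan does not say that they would then be coded as separate events for this search.

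**The case against.** Four points can be made for the plan.

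First, criterion 3 and the 13.3 heading both ask for at least two sites. A reader might infer that, by the plan's definition, one swollen gland plus fever is DRESS. The documents do not support that: the definition excludes it, and only the search fails to apply the definition. This stands and limits the lymph-node example. It does not touch the blood-count and febrile neutropenia examples.

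Second, a reader might infer that a reported DRESS disappears from the report. It does not. It remains in the TEAE tables by system organ class and preferred term, in the adverse event listings, and in the serious event tables if serious. It is also found in this category when two other criteria are separately recorded. What can be lost is its place in the special-interest output.

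Third, the list may be a deliberately sensitive screen that treats blood and lymphatic disorders as an organ group. That is a legitimate choice, and it would be wrong to say that such cases have no organ involved. It does not explain why the same event should also fill a second criterion, and a sensitive screen would not leave out the diagnosis itself.

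Fourth, the category is descriptive. The early-termination addendum keeps TEAE reporting as set out in the SAP but does not name the special-interest tables, so their production is an inference. This stands and limits the importance of the point.

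**Conclusion.** Wrong as written. The overlaps and the single credit for the DRESS term follow directly from the lists, with no assumption about event rates. Two findings can reach the threshold of three, and a reported DRESS scores 1 of 5 on its own.

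The effect is limited to one of 14 descriptive special-interest categories. No hypothesis test or efficacy result depends on it. It would be tempting to attach an expected number of false cases, but the documents give no rates of fever, lymph-node or blood-count events, and the planned number of patients was not recruited, so no such figure is offered.

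The conclusion assumes that the appendix is programmed literally and that no unwritten medical review follows. A reviewer checking each selected patient could remove false cases, but would not see a reported DRESS that had been filtered out beforehand.

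**What to change.** In SAP Appendix 13:

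1. State that one event, together with its own laboratory value, can satisfy only one criterion. Keep the blood and lymph-node terms in 13.2. Deleting them could lose true cases, because 13.4 reads laboratory values only and SAP Section 12.7.3 schedules these at Screening and Day 21 of each period. A blood event reported without a matching value would then score nothing.
2. Make the 13.3 search apply its heading: terms at two different sites, or a generalized term. Where the coded term carries no site, the investigator's term, which is already listed, can be read.
3. Select any event coded to the DRESS preferred term directly for this category, whatever else is recorded, and show in the listing which criteria were also met.

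The cost is three sentences of appendix wording and a small programming change. No new data are needed and no efficacy analysis is affected. The change should be fixed before unblinding, or reported as a labelled additional run if the table already exists.
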